The purpose of this single blinded, randomized, controlled, superiority trial is to compare the efficacy of an ultrasonic bone scalpel with standard of care surgical instruments during posterior spine fusion with instrumentation. The primary aim of this study is to compare differences in estimated blood loss per fusion level (EBL/level) between groups ($\theta = \theta_{standard\ care} - \theta_{USBS}$). We aim to test the null hypothesis that the difference between groups is less than or equal to 0 ($H_0: \theta \leq 0$). Based on a previous retrospective cohort study in a similar target population[21], we anticipate the EBL/level in the proposed study will be 48 mL/level (± 30) in the USBS group (θ_{USBS}) and 72 mL/level (± 28) in the standard instrument group ($\theta_{standard\ care}$). Although there are no universally established thresholds for defining a clinically meaningful difference in

EBL/level, the investigators are confident that the 33% reduction in blood loss per level observed in the previous study is representative of a clinically meaningful reduction in blood loss ($H_+ \theta \geq 24$ or $H_+ \theta \geq 33\%$). Based on a symmetric two sided, two stage group sequential design with O'Brien-Fleming stopping criteria and an alpha level of 0.05, we determined that a sample size of 62 subjects (31 subjects per group) would provide 90% power to reject the null hypothesis of no difference between groups (See Trial Monitoring section for information about the stopping criteria). This estimate assumes a group difference of 24 mL/level and a standard deviation of ± 28 in the standard instrument group and a standard deviation of ± 30 in the USBS group. Assuming a dropout rate of approximately 15%, we intend to enroll 36 subjects per group to achieve the desired statistical power. The estimated dropout rate is based on previous studies in a similar patient population, adolescents with idiopathic scoliosis.

b. Subject Screening:

All surgical patients under the care of two high volume pediatric orthopedic surgeons will be screened for study eligibility. All patients who elect to undergo spinal surgery at Children's Hospital Colorado under the care of the investigators of this study will be screened for study eligibility by the research coordinator (research assistant). Patients who are determined to meet the inclusion and exclusion criteria from above will be approached by the study team.

c. Enrollment and Consent:

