An intent to treat analysis of all randomized subjects will be performed. Descriptive statistics will be used to compare the distribution of demographics and clinical characteristics in the two groups. Baseline covariates significantly different between groups will be considered as potential confounding variables in subsequent statistical models. The primary aim of this study is to compare differences in estimated blood loss per fusion level (EBL/level) between the USBS and standard of care groups ($\theta = \theta_{USBS} - \theta_{standard\ care}$). We aim to test the null hypothesis that the difference between groups is less than or equal to 0 ($H_0: \theta \geq 0$). An independent sample t-test or multiple variable linear regression analysis, as appropriate, will be used to compare total EBL/level in the two study groups. For the secondary outcome variables, Chi-square tests will be used to compare differences in the categorical variables (the risk of adverse events, proportion of subjects meeting the intra-operative blood transfusion criteria) between the groups. Independent sample t-tests or Wilcoxon rank sum tests will be used to compare differences in the continuous variables (operative time, post-operative length of stay, and intraoperative irrigation volume).

e. Trial Monitoring/Human Subjects Research Consideration

Data Safety and Quality - All data will be collected and stored in a REDCap database. Access to the database will be restricted to investigators involved the study protocol per study personnel section of the COMIRB protocol application and/or the study delegation of duties log. Photographs obtained during surgery will be de-identified, assigned an appropriate study ID and will be stored on a secure departmental server that is managed by the IT department at Children's Hospital Colorado. The study coordinators will review data stored in the REDCap database on an ongoing basis. Potential outliers and/or biologically implausible data points will be identified and reviewed on an individual basis with the Principal Investigator.

Safety Monitoring – Based on the advice of our clinical trial study design consultant, [name], a Data Safety Monitoring Board (DSMB) will review the safety and efficacy of the study. The DMSB will consist of an orthopaedic surgeon not directly

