Decision/Stopping Criteria- This study will utilize a two-stage, group sequential design to monitor study progress. Under the alternative hypothesis, the two sided rejection boundaries at Stage 1 and Stage 2 were calculated according to the O'Brien-Fleming method (see Figures below). After 16 subjects per group have been enrolled, an interim analysis will be performed (Stage 1). If the standardized Z statistic representing the difference in estimated blood loss ($\hat{\theta} = \hat{\theta}_{standard\ care} - \hat{\theta}_{USBS}$) exceeds the upper or lower rejection boundary ($Z > 2.7965$ or $Z < -2.7965$), the trial will be stopped. Assuming the standard deviation of blood loss per level fused is 30 in the USBS group and 28 in the standard group, the trial will stop if $\hat{\theta} > 29.2$ mL/level or $\hat{\theta} < -29.2$ mL/level. If blood loss per level fused does not exceed the rejection bounds, the trial will continue until a total of 62 subjects have been enrolled (31 per group). At stage 2, the standardized Z statistic will be compared to the rejection bounds ($Z > 1.9774$ or $Z < -1.9774$). Assuming the standard deviation of blood loss per level fused is 30 in the USBS group and 28 in the standard group, we will conclude the USBS is superior to standard care instrument if $\hat{\theta} > 14.6$ mL/level or inferior to standard care instruments if $\hat{\theta} < -14.6$ mL/level. Sample size and stopping criteria were estimated using the RCTDesign package, R 3.1.2 (R Foundation of Statistical Computing, Vienna, Austria).

Summary of Decision Criteria - The decision criteria and potential corresponding conclusions are described in the table below.

Stage	Enrollment	Stop For Harm			Stop for Benefit		
		$\hat{\theta}_{\dagger}$	95% CI	pvalue*	$\hat{\theta}_{\dagger}$	95% CI	pvalue**
Stage 1	50%	-27.1	-42.2 to -8.55	0.005	27.1	8.55 to 42.2	0.005

Stage 2	100%	-13.9	-29.01 to 0.00	0.05	13.9	0.00 to 29.01	0.050
*Probability reject $\theta \geq 0$							
**Probability reject $\theta \leq 0$							
†Bias adjusted mean							

Figure 1. Plots of Rejection Boundaries (Red Lines) at Stage 1 and Stage 2 Relative to a Fixed Sample Design (Black Lines). 1.A Displays Rejection Boundaries on the Z Scale 1.B Displays Rejection Boundaries in Terms of EBL/level.

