Probability of Stopping at the Interim Analysis To aid in the interpretation of the stopping criteria, the probability of stopping the trial at the interim analysis (for benefit or harm), under hypothetical scenarios in which theta is known, has been estimated in the table below.

True θ	Probability of Stopping for Harm	Probability of Stopping for Benefit
---------------	----------------------------------	-------------------------------------

-29	0.4930	0.0000
-14	0.0729	0.0000
0	0.0050	0.0050
14	0.0000	0.0729
29	0.0000	0.4930

Power/Type I Error Rate The power and type I error rate associated with this group sequential design, under hypothetical situations in which theta is known, is outlined in the table below.

True θ	Power for Lower Rejection Boundary	Power for Upper Rejection Boundary
-29	0.975	0.000
-14	0.470	0.000
0*	0.025	0.0250
14	0.000	0.470
29	0.000	0.975

*Under null hypothesis ($\theta = 0$), the design maintains a type I error rate of 0.05.

f. Summarize Knowledge to be Gained

This study will help to identify any potential advantages and disadvantages with regard to the use of an ultrasonic bone scalpel used in posterior spinal fusion surgery for patients diagnosed with Adolescent Idiopathic Scoliosis. A better understanding of the intraoperative outcomes such as estimated blood loss and surgical time compared between the two groups could reveal if one technique is able to provide significantly better results during surgery. If one method is determined to be more effective or efficient than the other, then it could have a positive impact on spinal fusion surgery. Decreased blood loss could lead to decreased need of intraoperative and postoperative transfusions and the risks associated with them. Further, shorter operative time would decrease wound exposure time, which could have an effect on postoperative complications. Decreased operative time could also decrease the financial burden of surgery.

V. References

1. Shapiro, F. and N. Sethna, *Blood loss in pediatric spine surgery*. Eur Spine J, 2004. **13 Suppl 1**: p. S6-17.
2. Thompson, M.E., et al., *Predicting excessive hemorrhage in adolescent idiopathic scoliosis patients undergoing posterior spinal instrumentation and fusion*. Spine J, 2014. **14(8)**: p. 1392-8.

3. Diab, M., et al., *Use and outcomes of wound drain in spinal fusion for adolescent idiopathic scoliosis*. Spine (Phila Pa 1976), 2012. **37**(11): p. 966-73.

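### The stopping rule does not say which SD standardizes Z (type I error is about 0.057, not 0.05, if it is estimated), and two tables print two-direction values as one-direction values

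*Combined protocol and SAP*

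**What the plan says.** Section III.e, Decision/Stopping Criteria, sets a two-stage O'Brien-Fleming rule on the Z scale. Stage 1 is timed as "After 16 subjects per group have been enrolled, an interim analysis will be performed (Stage 1"), and the trial stops if Z is beyond ±2.7965. At Stage 2, with 31 per group, "the standardized Z statistic will be compared to the rejection bounds" of ±1.9774. Each bound is also given in mL/level (29.2 and 14.6), introduced by "Assuming the standard deviation of blood loss per level fused is 30 in the USBS group and 28 in the standard group".

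Section III.d, Data Analysis Plan, names the primary test: "An independent sample t-test or multiple variable linear regression analysis, as appropriate, will be used to compare total EBL/level in the two study groups". Nothing links that test to the Z bounds.

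The Summary of Decision Criteria table gives p-values of 0.005 (Stage 1) and 0.05 (Stage 2), for harm and again for benefit. Its footnotes define each as a test of a one-direction null. The interim stopping table gives 0.0050 for harm and 0.0050 for benefit at theta = 0. The power table gives 0.025 per direction at theta = 0, with a footnote that "the design maintains a type I error rate of 0.05".

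The Power Analysis (section II.a) describes a symmetric two-sided design that "would provide 90% power to reject the null hypothesis of no difference between groups", but writes a one-sided null, with theta as standard care minus USBS. Section III.d reverses theta to USBS minus standard care. Its null is less than or equal to zero in words and theta ≥ 0 in symbols.

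**The concern.** The independent biostatistician applies this rule to an unblinded dataset at both looks. As written, it could be applied in three ways: Z with the assumed SDs, Z with estimated SDs, or a comparison of the observed difference with 29.2 or 14.6 mL/level. Z with the assumed SDs and the mL/level comparison are nearly the same rule. Z with estimated SDs is different: it can give another stop or continue decision on the same data, and it does not hold the stated 0.05 with the printed cut-offs.

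The tables exist to help the monitoring board interpret a boundary crossing. A p-value labelled as one-directional but printed as two-directional misstates the evidence at the boundary. The theta = 0 row misstates the chance of a false early stop.

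**Working it through.** **Inputs.** SDs 28 (standard) and 30 (USBS), difference 24 mL/level, 31 per group (section II.a). Interim at 16 per group, bounds 2.7965 and 1.9774 (section III.e).

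**1. The plan's figures with known SDs.** Z1 and Z2 are bivariate normal with correlation √(n1/n2). At information fraction 0.5, the O'Brien-Fleming constants for two-sided 0.05 solve to 2.7965 and 1.9774, as printed. Overall error is 0.0500 (0.0499 at 16 then 31). Power at 24 mL/level is 0.901, matching the stated 90%.

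**2. Bounds in mL/level.** SE = √((28² + 30²)/n) = √(1684/n).

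| n per group | SE | Bound (mL/level) |
|---|---|---|
| 15.5 | 10.423 | 2.7965 × 10.423 = 29.15 |
| 16 | 10.259 | 2.7965 × 10.259 = 28.69 |
| 31 | 7.370 | 1.9774 × 7.370 = 14.57 |

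The printed 29.2 therefore belongs to 15.5 per group. At the stated 16 it is 28.7.

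**3. Error when the SD is estimated.** For a single look, 2·P(t30 > 2.7965) = 0.0089 (normal: 0.0052), and 2·P(t60 > 1.9774) = 0.0526 (normal: 0.0480). Overall error was simulated with normal data, 16 then 31 per group:

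| Rule, theta = 0 | Stage 1 stop | Overall error |
|---|---|---|
| Estimated SD, printed Z bounds | 0.009 | 0.057 |
| Estimated SD, t bounds 3.017 (30 df) and 2.019 (60 df) | 0.0052 | 0.050 |

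The estimated-SD error was 0.0566 in a run of 1 million trials and 0.0569 in a run of 4 million.

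The t bounds carry over the same nominal two-sided p-values: 2·P(Z > 2.7965) = 0.00517 and 2·P(Z > 1.9774) = 0.0480.

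**4. Error if the mL/level values are used as fixed thresholds.** With 29.2 and 14.6, the error is 0.049 if the assumed SDs are true. As an illustration, it is 0.028 if both SDs are 10% smaller, 0.075 if 10% larger and 0.105 if 20% larger. At a true difference of 24 mL/level, estimated-SD Z and the 29.2 threshold disagree on stopping at Stage 1 in 10.3% of trials.

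**5. Decision table.** P(Z > 2.7965) = 0.0026 in one direction and 0.0052 in both, so the printed 0.005 is the two-direction value. At the Stage 2 bound the sequentially adjusted p-value is 0.025 in one direction and 0.05 in both. The table's own Stage 2 95% confidence limit of 0.00 agrees with 0.025 one-sided.

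**6. Interim stopping table.** Probability of stopping per direction, known SDs, half information:

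| True theta | Computed | Printed |
|---|---|---|
| 0 | 0.0026 | 0.0050 |
| 14 | 0.073 | 0.0729 |
| 29 | 0.494 | 0.4930 |

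Only the theta = 0 row is off, by 0.0050/0.00258 = 1.9-fold per side. The printed pair adds to 0.010, against a design value of 0.0052.

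**The case against.** The rule is stated on the Z scale at both stages. Each mL/level figure carries an explicit SD assumption, so it reads best as a translation and not as a second rule. That is fair: the error rates in step 4 illustrate misuse. The text does say the trial will stop at that value, however, so some ambiguity remains. The 10.3% also concerns Stage 1 decisions only; final reject or not-reject conclusions differ in about 2.6% of trials at 24 mL/level and 2.0% at zero.

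The excess error is under 0.01 and arises only if estimated SDs are combined with normal cut-offs; a t-test would ordinarily be read against a t distribution. This stands as a limit on size, but the plan prints only normal cut-offs and does not connect them to the t-test.

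The DSMB Charter, which was not available for this review, may name the SD. It could settle that question, but it cannot correct figures printed in the protocol.

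The table errors do not change a decision based on Z, and the theta = 0 row overstates the false-stop risk instead of hiding it. The 29.2 versus 28.7 gap is a rounding matter (half of 31 is 15.5). Section III.e fixes the direction of theta for the stopping rule, so the sign conflict is one of wording. All of this is accepted.

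**Conclusion.** The concern holds and should be fixed. The printed Z bounds are correct for known SDs, and the stated 0.05 is right in that case. If the SD is estimated, as the planned test implies, the same bounds give about 0.057 overall and 0.009 at Stage 1. This assumes normally distributed EBL/level, looks at 16 and 31 per group, and the unadjusted two-sample comparison.

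The decision-table p-values at both stages and the theta = 0 row of the stopping table are two-direction values presented as one-direction values. The other stopping rows, the printed bounds and the power table agree with the recalculation. The hypothesis and sign conflicts have no effect on the error rate, because the stopping rule fixes its own direction.

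**What to change.** - State that both looks use the planned primary test with the SD estimated from the data, and set the rule on the nominal two-sided p-value: below 0.00517 at Stage 1 and below 0.0480 at Stage 2. For the unadjusted t-test this is |t| > 3.017 on 30 df and > 2.019 on 60 df. If regression is used, take the model's residual df; with two single-df covariates such as surgeon and gender, for example, 3.034 on 28 df and 2.020 on 58 df.
- Say that the mL/level values are illustrative, and give 28.7 for Stage 1 at 16 per group.
- In the decision table, either print 0.0026 and 0.025 as one-sided, or label 0.005 and 0.05 as two-sided. In the second case, note that the Stage 2 value of 0.05 is sequentially adjusted and that the nominal cut-off is 0.0480.
- Change the theta = 0 row of the stopping table to 0.0026 and 0.0026.
- Define theta as standard care minus USBS throughout, with H0: theta = 0 tested two-sided (0.025 per direction).

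**Cost.** No extra patients, but this is more than relabelling if normal cut-offs were intended. With estimated SDs, simulated power at 24 mL/level goes from 0.899 (Z cut-offs) to 0.891 (t cut-offs), so the stated 90% should read about 89%. The chance of stopping early for benefit at 24 mL/level falls from 0.34 to 0.27.
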